### **Protection against Risks**

Studies involving BMAC and/or allograft have been completed in the past. The study by [name] has shown positive results of using allograft with BMAC for spinal fusions. The investigators are board certified orthopaedic spine surgeons and are familiar with the protocol and operating procedures. For data collection, the research coordinator is knowledgeable in the field of orthopaedic care and clinical research. All personnel have completed CITI training and the investigators have a dedicated staff and nurse to attend to the patient's medical and psychological needs if needed. If patients require medical monitoring, ancillary care, or equipment, patients will be able to seek care in case of an emergency at the NYU-HJD Immediate Care Center which is open 24/7. The PI and the research coordinator, [name], CRCC, will also be available to patients during regular office hours.

### Investigation schedule and follow-up

Data will be collected pre-operatively regarding individual patient demographics, radiographic images, laboratory values, and the surgical procedure to be performed. These data will be recorded onto a de-identified data collection sheet by the researchers. The patient data sheets will then be entered into a protected electronic database, while the data sheets will be stored as a back-up until the study is complete. Once the completed database is analyzed and summarized, the results will be presented to the involved participants without any identifiable patient information. A Delegation of Duties log will be prepared and maintained in the study regulatory binder.

A separate surgeon and radiologist will be performing the radiographic analysis and an office medical assistant will have the patients fill out questionnaires and record any complications pertinent to the study. Follow-up will be the investigators' routine follow-up, which is 6 weeks, 3 months, 6 months, 1 year, and 2 years post-op.

PI: [name]

### Case Report Forms

# Pre-op visit

- Informed consent
  - ❖ If informed consent is not obtained at pre-operative visit, the visit will not continue.
- Pre-op investigator form
- Pre-op subject questionnaire

### 6-week follow-up

- Follow-up investigator form
- Follow-up subject questionnaire

### 3-month follow-up

- Follow-up investigator form
- Follow-up subject questionnaire

## 6-month follow-up

- Follow-up investigator form
- Follow-up subject questionnaire

### 1-year follow-up

- Follow-up investigator form
- Follow-up subject questionnaire

### 2-year follow-up

- Follow-up investigator form
- Follow-up subject questionnaire

# **Costs to the Subject**

All of the tests (i.e. physical evaluation and imaging components) will be performed as part of the standard of care. The patient may want to discuss this with his insurance carrier in advance. The patient will be responsible for any co-payments and/or deductibles for services rendered.

The patient or his/her insurance company will be responsible for paying for the 1-year follow-up CT scan because it is part of standard care. Patients will have the option to refuse CT scan in which case they will be excluded from the primary data analysis but will be part of the secondary analysis.

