### Preliminary Data

In an earlier study with unpublished results, 14 BMAC+allograft patients were compared to 3 ICBG. This randomized series determined radiographic fusion in 92.9% of cases among the BMAC+allograft and ICBG cohorts, suggesting no difference in fusion efficacy among these grafts. This study did not identify any difference between lumbar spinal fusion patients receiving ICBG versus BMAC+allograft during surgery, on the basis of patient-reported outcomes up to 1-year follow-up and fusion grading. Only higher SF-12 MCS scores at baseline among ICBG patients were sustained at 6-weeks and 6-months post-operative. These preliminary results are important given the controversy surrounding effective use of interbody grafts, but are not decisive especially when, for many surgeons, the choice is between BMP and BMAC.

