### • Arthodesis rate one year post-operation (paired t-test):

The effect size (ES) in this study was 0.4, considered to be low using Cohen's (1988) criteria. With an alpha = .05 and power = 0.80, the projected sample size needed with this effect size is approximately N = 23.

Thus, our proposed sample size of N=60 (with 20 patients per arm; effectively 40 for t-tests between groups) will be more than adequate for the main objective of this study and should also allow for expected attrition

Completion rate of enrolled patients in our protocol is estimated to be 85% based on standard clinical follow up rates for lumbar Spinal Fusion patients at the investigators practices. Therefore, by enrolling 20, we expect at least 17 in each group.

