# Aim 1: Clinical Study

This study will analyze the clinical and radiographic outcomes in terms of pre-operative measures, intra-operative measures, and post-operative measures followed-up for in the three groups.

Primary Outcome Endpoint: As per the primary outcome measure, fusion status at 1 year will be assessed via CT scan by an independent radiologist. Clinical outcomes will be defined by patient reported and health-related quality of life measures previously defined. Differences from preoperative visit to post-operative time points will be compared between the 3 groups by Student t-tests. Based on preliminary data, improvements are expected in these outcome measures: ODI from 33.42 (SD:6.22) to 26.75 (SD:8.19); SF-12 PCS from 29.00 (SD:6.05) to 31.42 (SD:6.05); SF-12 MCS from 31.42 (SD: 6.50) to 35.75 (SD: 13.82); NRS from 8.17 (SD: 1.27) to 5.93 (SD: 1.90). Multivariate regression analysis, controlling for age, sex, race, and charlson comorbidity index, will be performed to determine the effect of treatment on reaching MCID values, as defined in Parker et al 2012.[2]

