### **6.** Criteria for Action

- Subject stopping will occur if any adverse events occur that are level 4 or above, or if the subject is unlikely to comply with the follow-up evaluation schedule
- Study stopping will occur if there is a case of mortality. DSMB and IRB review will determine continuation or termination of study.
- Study stopping will occur if there is a greater than normal rate of morbidity as determined by the monitoring entity; the study subject will be un-blinded and the rates of morbidity will be observed for that subject to determine the cause. Acute vs. Subacute vs chronic morbidity complications vary in degree of prevalence, still greater

PI: [name]

than 10-15% complication rate will deviate from the literature anticipated (Hoffmann 2013, Ajiboye 2016). Study stopping will occur if there is a greater prevalence of pseudarthrosis in the BMAC study group; Lumbar pseudarthrosis rates with use of BMP have been estimated to 6.4% in single center studies. (Kim 2013). Similar percentages can be deduced from reported lumbar arthrodesis rates in larger review studies. Use in lumbar fusions showed a 94% arthrodesis average rate for BMP-2, and 85% average arthrodesis rate using bone marrow aspirate (Chun 2015). For these reasons a pseudarthrosis rate of greater than 10-15% would warrant action.

- Study should be stopped if there is a 10% reduction in fusion rates in the studied group relative to the control group which is the current "Gold Standard" of Iliac Crest graft.

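### Patients who refuse the 1-year CT leave the primary fusion analysis, and no rule says how stopped or revised patients are counted

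*Combined protocol and SAP*

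**What the plan says.** Aim 1: Clinical Study sets the primary outcome: "fusion status at 1 year will be assessed via CT scan by an independent radiologist". Costs to the Subject states that "The patient or his/her insurance company will be responsible for paying for the 1-year follow-up CT scan", and that patients may "refuse CT scan in which case they will be excluded from the primary data analysis but will be part of the secondary analysis". No section says what the secondary analysis consists of.

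Criteria for Action (section 6 of Data Monitoring) gives the rule for single patients: "Subject stopping will occur if any adverse events occur that are level 4 or above, or if the subject is unlikely to comply". Compliance here means keeping to the planned visits. That section does not say whether a stopped subject's outcomes are still collected or analysed. Document of Consent allows withdrawal at any time and is equally silent. Revision surgery is named only as a risk, under Adverse Events/Risks, and is not linked to the endpoint.

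The Data analysis plan has one general sentence on missing data, which allows imputation where appropriate. It names no method, variables or conditions. No analysis set, such as all randomised patients, is defined anywhere.

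**The concern.** The rule on CT refusal is a written exclusion from the primary analysis, not just an omission. Followed exactly, it compares fusion among patients who accepted a scan rather than among those randomised. A patient who feels well may see no reason to pay for a CT, and a patient who is doing badly may have left the practice. If such reasons differ between arms, the comparison is no longer protected by randomisation. Follow-up questionnaires may show whether refusers differ clinically, but not whether they fused.

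The missing rule for stopped and revised patients adds to this. A patient reoperated for non-union before the CT is a clear failure of fusion. Under the present text that patient could be counted as not fused, treated as missing, left out, or judged on a scan taken after the second operation. The choice could be made after the data are seen. Since few non-unions are expected, one patient can change an arm's result visibly.

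**Working it through.** **Inputs.** Sample Size Analysis: 20 patients per arm, 85% completion, and "by enrolling 20, we expect at least 17 in each group". Criteria for Action: "94% arthrodesis average rate for BMP-2, and 85% average arthrodesis rate using bone marrow aspirate". Preliminary Data: "radiographic fusion in 92.9% of cases among the BMAC+allograft and ICBG cohorts". The 85% figure is for marrow aspirate, not for BMAC with allograft. The CT refusal, stopping and revision rates are not given.

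**The plan's own figure.** 20 × 0.85 = 17, so the stated 17 per arm reproduces. It leaves 3 of 20 without complete follow-up from all causes, with no separate allowance for patients who attend but refuse the CT.

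**Expected non-unions per 20 patients**, 20 × (1 − fusion rate):
- at 94%: 20 × 0.06 = 1.2
- at 92.9%: 20 × 0.071 = 1.4
- at 85%: 20 × 0.15 = 3.0

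**Extreme bounds.** Let m of 20 CTs be missing in each of two arms, with every scanned patient fused. Each arm's rate then lies between (20 − m)/20 and 20/20, so the difference lies between −m/20 and +m/20:
- m = 1: ±5 points
- m = 2: ±10 points
- m = 3: ±15 points

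For a single arm with 16 of 17 scanned patients fused (94.1%) and 3 unscanned, the rate over all 20 lies between 16/20 = 80% and 19/20 = 95%.

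**One revised patient (hypothetical counts).** Suppose 16 patients are scanned and all are fused, and a seventeenth was reoperated for non-union before the CT. Leaving that patient out gives 16/16 = 100%; counting the patient as not fused gives 16/17 = 94.1%.

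**Sampling error**, at 94% against 85%:
- 20 per arm: 1.96 × √(0.85×0.15/20 + 0.94×0.06/20) = 1.96 × 0.0959 = 18.8 points
- 17 per arm: 1.96 × √(0.85×0.15/17 + 0.94×0.06/17) = 1.96 × 0.1040 = 20.4 points

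**Illustration of selective loss (assumptions, not figures from the documents).** Let a share L of an arm have no CT, with non-unions lost k times as often as fused patients. The loss among fused patients is a = L/(p + (1 − p)k), and the observed fusion rate is p(1 − a)/(1 − L). Take k = 3 and L = 0.15:
- p = 0.85: a = 0.15/1.30 = 0.115, observed 88.5%
- p = 0.94: a = 0.15/1.12 = 0.134, observed 95.8%

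The true gap of 9.0 points is then seen as 7.3 if this holds in both arms, 5.5 if only in the 85% arm, and 10.8 if only in the 94% arm. The largest shift is 3.5 points, and it can go either way.

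**The case against.** The plan has safeguards. The 1-year CT is described as standard of care, exclusion criterion 12 removes patients unlikely to keep to follow-up, consent is meant to secure commitment to all visits, and a research assistant must see that CTs are taken. These make few missing scans likely. They do not say how the missing ones are handled.

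The bounds are extremes. Reaching −10 points with two missing per arm needs both missing patients in one arm unfused and both in the other fused. At 85% against 94% with no selective loss, the chance of that pattern against the 85% arm is 0.15² × 0.94² = 2%. With non-unions lost three times as often, the unfused share among missing patients is 0.45/1.30 = 35% and 0.18/1.12 = 16%, and the chance is about 8%. This stands: the bounds describe what the data could not exclude, not what is expected.

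The modelled shifts are also far below sampling error. That limits the practical harm, but the reported interval covers chance only, not selective exclusion.

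A reader might go further in four ways that the documents do not support:
- That refusal is known to come a year after randomisation and to follow outcome. The text gives no time; refusal could be declared at consent, before arm or outcome is known.
- That two missing scans per arm could trigger the rule that the "Study should be stopped if there is a 10% reduction in fusion rates in the studied group relative to the control group". That rule compares with the iliac-crest control, whereas the rates used above are for BMP-2 and marrow aspirate. It is a monitoring rule and not a yardstick for this bias.
- That the conflict between sections on whether patients are blinded settles the matter. It needs its own correction, and refusal driven by symptoms or cost does not depend on it.
- That multiple imputation is needed. With about 1 to 3 non-unions per arm an imputation model would have little support.

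**Conclusion.** The point holds in a limited form and should be fixed. The plan excludes CT refusers from its primary endpoint, leaves the secondary analysis undefined, and gives no rule for stopped patients or for those revised before the CT. The general imputation sentence does not resolve this, because it names no method and sits beside a specific exclusion.

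This makes bias possible, not shown. Its size and direction are unknown because no refusal, stopping or revision rate is given, and it may be nil. A reader might infer that the fusion comparison will favour one graft; nothing in the documents supports a direction. What can be stated is the scale: 1.2 to 3.0 expected non-unions per 20 patients, and extreme bounds of ±5 to ±15 points for 1 to 3 missing CTs per arm, against sampling error of about ±19 to 20 points. The expected counts assume that the cited fusion rates apply here, and the bounds assume that all scanned patients are fused. Confidence is medium.

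**What to change.** 1. In Costs to the Subject and Aim 1, replace the exclusion with text to this effect: *All randomised patients are accounted for in the arm assigned. Reoperation for non-union before the 1-year CT counts as not fused. The result in patients with a known fusion outcome is reported together with two mandatory sensitivity analyses: missing counted as not fused, and best- and worst-case bounds for each pairwise difference. The number of missing CTs and the reasons are given by arm.* Multiple imputation may be added but is not required.
2. State what the secondary analysis is: which outcomes, which patients and which comparisons.
3. In Criteria for Action, state that stopping a subject does not end outcome collection to which the patient consents, and does not remove the patient from the analysis. The clinical criteria for stopping stay as they are.

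The cost is wording and slightly more analysis work, with no visits or scans beyond those already called routine. Reported uncertainty will be wider, and fusion rates may come out slightly lower because revised patients count as failures. The CT result that the sponsor planned is still reported for patients with a known outcome.

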# **Payment for Participation**

Subjects will not be compensated for participation in this study.

This clinical trial will be posted on clinicaltrials.gov

PI: [name]

# **Data Analysis**

### Sample Size Justification

There are no previous studies with exact means in ODI for a BMAC group not the association between clinical outcomes and concentration of MSCs and CFUs. Therefore, assumptions had to be made. If the standard deviation for each group was assumed to be 10 and equivalence as within 12.8 (MCID), given 90% power and alpha=0.05, we would need 14 patients per group. However, if we assume equivalence as within 6 points, we would need 59 patients per group. We understand that assumptions greatly affect sample size, and therefore, our desired sample size of 60 patients is appropriate.

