# Our hypothesis is that:

For patients who undergo lumbar spinal fusion surgery with interbody support, the outcomes in terms of pre-operative measures, intra-operative measures, and post-operative measures in the investigational group (BMAC + allograft) will be similar to the compared BMP group and control group at 24 months postoperatively.

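### The 12.8-point ODI equivalence band behind the sample size is 1.9 times the ODI improvement the protocol expects, so it cannot exclude complete loss of that benefit

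*Combined protocol and SAP*

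**What the plan says.** The hypothesis section predicts that outcomes with BMAC plus allograft "will be similar to the compared BMP group and control group at 24 months postoperatively". ODI is one of those outcomes.

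The Sample Size Justification under Data Analysis gives two ODI scenarios.
- The first begins "If the standard deviation for each group was assumed to be 10 and equivalence as within 12.8 (MCID") and continues "given 90% power and alpha=0.05, we would need 14 patients per group".
- The second is that "if we assume equivalence as within 6 points, we would need 59 patients per group".

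The section chooses neither, notes that the result depends heavily on the assumptions, and concludes that "our desired sample size of 60 patients is appropriate". The 60 is a total: the earlier Sample Size Analysis section describes it as "our proposed sample size of N=60 (with 20 patients per arm; effectively 40 for t-tests between groups") and expects at least 17 completers per arm. That section has its own justification, based on arthrodesis rate, which is not examined here.

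Aim 1 gives the only expected ODI change in the document: "improvements are expected in these outcome measures: ODI from 33.42 (SD:6.22) to 26.75 (SD:8.19"). It attributes this to preliminary data. It makes CT fusion at 1 year the primary outcome and compares changes from baseline between arms by Student t-tests. It names no equivalence test and no margin.

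**The concern.** An equivalence band states how large a true difference between arms may be and still be treated as unimportant. It should be smaller than the benefit the treatments are expected to deliver. Otherwise a finding of equivalence is compatible with one treatment delivering nothing.

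Here the band is set at the MCID. Aim 1 uses MCID as a threshold for treatment success, but the Sample Size Justification uses it as a tolerated gap between arms, and no reason is given why a gap of that size would be acceptable. Set against the protocol's own expected change, the band is wider than the whole expected benefit.

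What is at stake is the meaning of the word similar for ODI. If the report leaned on the 12.8-point definition, it could call disability outcomes similar in two arms of which only one had improved.

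**Working it through.** **Inputs**
- Bands 12.8 and 6 points, SD 10, 90% power, alpha 0.05, stated sizes 14 and 59 per group: Sample Size Justification.
- ODI 33.42 (SD 6.22) before and 26.75 (SD 8.19) after: Aim 1.
- 20 per arm, about 17 completing: Sample Size Analysis.

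**1. Reproduce the plan's figures**

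Two one-sided 5% tests, arms truly equal, normal approximation: n = 2 × [SD × (z0.95 + z0.95) / band]².
- Band 12.8: 2 × (10 × 3.290 / 12.8)² = 13.2, so 14.
- Band 6: 2 × (10 × 3.290 / 6)² = 60.1, so 61.

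The ordinary two-sided formula, 2 × [SD × (1.960 + 1.282) / band]², gives 13 and 59; its t-based version gives 14 and 60. The stated 14 and 59 are therefore reproduced within two patients, and there is no arithmetic error in them.

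**2. Compare the bands with the expected benefit**
- Expected improvement: 33.42 − 26.75 = 6.67.
- 12.8 / 6.67 = 1.92.
- A no-change arm against an arm that improves as expected: difference 6.67, inside ±12.8.
- Worsening that still fits: 12.8 − 6.67 = 6.13 points.
- For the 6-point band, 6 / 6.67 = 0.90. A no-change arm falls outside it by 0.67 points.

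**3. Which band the trial can support**

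Twenty per arm (17 completing) exceeds 14 but is far below 59. Simulated power to show equivalence for truly equal arms, two one-sided 5% tests, SD 10:

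| Band | 17 per arm | 20 per arm |
|---|---|---|
| 12.8 | 96% | 98% |
| 6 | 10% | 18% |

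Only the 12.8-point scenario is workable at this size.

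**4. Chance that a no-benefit arm would pass**

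This assumes a true difference of 6.67 and a rule that the CI must lie inside the band. The rule is an assumption, because the plan states none. Simulated results at 12.8:

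| SD | CI | 17 per arm | 20 per arm |
|---|---|---|---|
| 10 | 90% | 54% | 60% |
| 10 | 95% | 41% | 47% |
| 8.19 | 90% | 69% | 75% |
| 8.19 | 95% | 56% | 64% |

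At the 6-point band, with a 90% CI, the same arm passes less than 3% of the time at either SD and either size.

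**5. Precision available**

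95% CI half-width = t × SD × √(2/n), with SD 10:
- n = 17: 2.037 × 10 × √(2/17) = 6.99
- n = 20: 2.024 × 10 × √(2/20) = 6.40

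Both are about the size of the whole 6.67-point improvement. With the Aim 1 follow-up SD of 8.19 they become 5.7 and 5.2, still 86% and 79% of it.

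**6. Would a narrower band rescue an equivalence claim?**

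A band equal to the full expected benefit, 6.67, would need about 48-49 per group at SD 10 and 90% power. Any band that preserved part of the benefit would need more.

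**The case against.** **No decision rule uses 12.8.** It appears only as one of two conditional sample-size scenarios, and the analysis plan tests ODI changes with Student t-tests. This stands. A reader might infer that the trial will declare a useless graft equivalent; the documents do not support that. The pass rates above describe a test the plan does not name, and even under that test passing is far from certain: at SD 10 with a 95% CI, a no-benefit arm fails more often than it passes.

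**The 6-point scenario excludes a no-benefit arm.** True, but the planned size cannot support it, so it does not rescue the rationale.

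**The 6.67 is a weak benchmark.** Aim 1 gives no arm, time point or number of patients. The one earlier study described under Preliminary Data had 14 BMAC and 3 iliac crest patients and no BMP arm. Eligibility requires ODI above 30%, yet a mean of 33.42 with SD 6.22 puts about 29% of patients below 30 if scores are normal ((30 − 33.42) / 6.22 = −0.55). This also stands and limits confidence in the exact ratio. It does not reverse the conclusion: for the band to exclude a no-benefit arm, the expected improvement would have to exceed 12.8, nearly double the only figure given.

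**A graft that failed to help would be noticed.** CT fusion is primary, there are stopping criteria for fusion and pseudarthrosis, and questionnaires are reviewed for worsening. This is fair. A reader might infer that the trial's overall endorsement of a graft depends on the ODI band; it does not.

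**Responder rates.** A reader might also infer that few patients can reach the MCID in the Aim 1 regression. Aim 1 takes its MCID values from a cited source and does not state 12.8 there, so that step is not supported.

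**Conclusion.** The point holds as a flaw in the ODI sample-size rationale and in any conclusion of similar ODI. By the protocol's own figures, the only ODI band that 17-20 per arm can support is 1.9 times the expected improvement, so it cannot exclude complete loss of that benefit, or a worsening of up to 6.1 points. If that band were used in a test, an arm with no benefit would pass in roughly 41-75% of trials, depending on the SD (8.19 or 10), the number per arm and the CI level.

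This assumes that the 6.67-point improvement applies to the comparator arm at the time of comparison and that the SD of the analysed ODI outcome is near 8-10. It does not touch the fusion analysis, and it does not show that the trial would in fact declare equivalence.

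**What to change.** - **Sample Size Justification:** remove 12.8 as the definition of ODI equivalence. State instead that 17-20 per arm gives a 95% CI half-width of about 6.4-7.0 points for a between-arm ODI difference (SD 10), which is about the size of the whole expected improvement.
- **Aim 1:** state that between-arm ODI differences will be reported as estimates with 95% CIs, and that no ODI equivalence or similarity claim will be made. Give the arm and time point behind the 33.42 and 26.75.
- **Hypothesis section:** make the same restriction, so that the prediction of similarity is not carried over to an ODI conclusion.

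Substituting a narrower band is not a practical alternative at this size, as step 6 of the working shows.

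The cost is wording, with no extra patients. The downside is real: the ODI conclusion becomes an estimate with its interval rather than a statement of similarity, and the 60 patients no longer have an ODI power calculation behind them, only a statement of precision.

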### **Human Subject (Inclusion/Exclusion Criteria)**

#### **Inclusion criteria:**

- 1. Must be 18 years old or older
- 2. Scheduled for elective posterior or anterior and posterior spinal fusion of the lumbar spine with or without anterior interbody support
- 3. Failed at least 6 weeks of conservative care
- 4. ODI v2.1 score > 30%
- 5. No contraindication to BMAC (as per manufacturer)
- 6. Signed consent form

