# **Research Design & Methods**

Subjects who are candidates for lumbar spinal fusion with interbody support will be screened for inclusion in the study. All procedures are approved by the FDA (see appendix A for approved labeling) and are common practice at NYULMC. If the subject meets all of the eligibility criteria

PI: [name]

and agrees to participate in the study after informed consent, they will be enrolled into one of the three arms.

An enrollment ratio of BMAC + allograft to BMP to Autograft with bone marrow aspirate (control) (1:1:1) for a total of 60 subjects to be enrolled in the study. The study will determine and compare differences in fusion rate and health related quality of life parameters at 6 weeks, 3 months, 6 months, 1 year, and 2 years postoperatively.

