# Subject Identification, Recruitment and Consent

As part of the standard of care, the subject will have an initial consultation with the PI/MD which includes appropriate physical and radiographic examinations. The subject will be informed of the nature of their spinal disease and treatment options, operative and conservation non operative care. Should the surgeon feel that operative treatment is the best option, they will be eligible for enrollment into this study. Their treatment will not be influenced by the existence of this study.

All study participants will be patients of [name]. The same care will be provided independent of the patient's willingness to be a part of the study. The 60 subjects to be accrued are based on investigator's caseloads. Only patients who are able to understand the English language will be allowed to participate in the study due to the nature of the validated questionnaires that will be given to them.

PI will identify his clinic patient's eligibility for enrollment into the study using inclusion/exclusion criteria. Should the PI/surgeon feel that operative treatment is the best option, subject will be eligible for enrollment into this study. Their treatment will not be influenced by the existence of this study. PI anticipates to enroll up to 4 patients per month, allowing for completion of enrollment in 15 months, but no longer than 2 years.

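### The ODI justification gives 14 or 59 patients per group depending on the margin, then calls a three-arm total of 60 appropriate without choosing one; 20 per arm meets 12.8 points but not 6

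*Combined protocol and SAP*

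**What the plan says.** The Sample Size Justification under Data Analysis is built on ODI. It assumes an SD of 10 in each group, 90% power and alpha 0.05. For equivalence within 12.8, which it labels the MCID, it gives 14 patients per group. It continues: "However, if we assume equivalence as within 6 points, we would need 59 patients per group". It closes: "We understand that assumptions greatly affect sample size, and therefore, our desired sample size of 60 patients is appropriate". It does not say which margin is adopted or whether 60 is per group or in total.

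Other sections settle the second question. Research Design & Methods describes 1:1:1 enrolment "for a total of 60 subjects to be enrolled in the study". The earlier Sample Size Analysis puts 20 patients in each arm, assumes 85% completion, and adds: "Therefore, by enrolling 20, we expect at least 17 in each group".

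On analysis, Aim 1 makes fusion on CT at 1 year the primary outcome. For the clinical outcomes it states: "Differences from preoperative visit to post-operative time points will be compared between the 3 groups by Student t-tests". It also plans a multivariate regression on reaching MCID values. It expects "ODI from 33.42 (SD:6.22) to 26.75 (SD:8.19"). The hypothesis section expects the BMAC arm to resemble both other arms at 24 months. No section sets an ODI equivalence margin or decision rule.

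**The concern.** The two per-group sizes differ about fourfold, and the choice between them is the choice of margin. The paragraph leaves that choice open and goes straight to 60. Because 60 follows closely on 59 per group, the closing sentence can look as if the stricter scenario were met, when each arm has about a third of that number.

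What is at stake is how the ODI result will be read. The hypothesis is one of similarity and the sizing is for equivalence, but the planned comparison is a test of difference, plus a responder regression that sets no equivalence rule either. With no named margin, a reader of the results cannot tell how large an ODI difference the trial was able to exclude.

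**Working it through.** **Inputs.** SD 10, margins 12.8 and 6, 90% power, alpha 0.05 (Sample Size Justification); 20 per arm, 85% completion, 17 completers (Sample Size Analysis); ODI SDs 6.22 and 8.19 (Aim 1). The plan gives neither the sidedness of alpha nor the true difference. I assume a true difference of 0 and two one-sided tests (TOST) at 0.05 each, and show alternatives where they matter.

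**1. The plan's own figures, per group, SD 10, 90% power.**

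- TOST, normal formula, n = 2[SD(1.645 + 1.645)/margin]²: 13.2 → 14 at 12.8; 60.1 → 61 at 6. The exact-t version also gives 14 and 61.
- Two-sided 0.05 normal formula, n = 2[SD(1.960 + 1.282)/margin]²: 12.8 → 13; 58.4 → 59.
- Two-sided two-sample t-test: 13.9 → 14; 59.4 → 60.

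The stated 14 and 59 are sound, within two patients on each method.

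**2. Per group to total.**

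| Margin | Per group | Evaluable, 3 arms | Enrolled at 85% completion |
|---|---|---|---|
| 12.8 | 14 | 42 | 14/0.85 = 16.5 → 17 per arm, 51 |
| 6 | 59 | 177 | 59/0.85 = 69.4 → 70 per arm, 210 |

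Planned: 60 enrolled, about 3 × 17 = 51 evaluable.

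**3. TOST power per pairwise comparison** (t critical values, integrated over the distribution of the pooled SD).

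| SD | Margin | 20 per arm | 17 per arm |
|---|---|---|---|
| 10 | 12.8 | 98% | 96% |
| 10 | 6 | 18% | 10% |
| 12 | 12.8 | 90% | 84% |
| 15 | 12.8 | 69% | 57% |
| 8.19 | 6 | 47% | 35% |
| 6.22 | 6 | 82% | 73% |

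SDs of 12 and 15 are my sensitivity values; 8.19 and 6.22 are Aim 1's, if they are on the same scale. At one-sided 0.025 and SD 10, power is 95% and 90% at 12.8 points, and 4% and 1% at 6.

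The reason for the low power at 6 points is simple. At SD 10 the standard error of a difference is 10√(2/20) = 3.16, or 10√(2/17) = 3.43. The half-width of a 90% interval is then about 1.686 × 3.16 = 5.3, or 1.694 × 3.43 = 5.8. The observed difference would have to lie within about 0.7 or 0.2 points of zero for the interval to fit inside ±6.

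**4. Smallest margin with 90% power at SD 10:** 10.6 points (20 per arm) or 11.5 points (17).

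**5. SD needed for 90% power at 6 points:** 5.7 or less (20 per arm) or 5.2 or less (17). If change scores are compared, Aim 1's SDs give SD² = 6.22² + 8.19² − 2r(6.22)(8.19) = 105.76 − 101.88r. That requires a pre-post correlation r of about 0.72 or 0.77, which the plan does not give. At r = 0.5 the SD is 7.4 and power at 6 points is 62% or 50%.

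**6. The planned t-test.** At SD 10 its power to detect a true 6-point difference is 46% (20 per arm) or 40% (17), so such a difference would be non-significant in 54% or 60% of trials.

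**7. The margin against the expected change.** Aim 1 expects ODI to fall by 33.42 − 26.75 = 6.67. If the scales match, 12.8/6.67 = 1.9, so the margin that 60 patients can support is nearly twice the whole expected improvement.

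**The case against.** The best defence is that nothing stated is numerically wrong. Sixty patients cover the 12.8-point scenario with attrition. That figure is labelled the MCID, and MCID is the one clinical threshold in Aim 1, so 12.8 is the more natural reading. The 6-point line may be only an illustration of how sensitive the size is to assumptions. ODI is secondary. All of this stands, but the text never says that 12.8 is the margin, and its conclusion rests on no stated choice.

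Four stronger readings are tempting and are not supported:

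- A reader might infer that the plan claims 60 patients meet the 6-point margin, or took 59 per group for a total. It makes no such claim, and other sections state plainly that 60 is the total.
- A reader might infer that non-significant t-tests will be reported as equivalence. The plan does not say how they will be read; the risk comes from its silence together with the similarity hypothesis.
- A reader might see a rival basis for the size in "The 60 subjects to be accrued are based on investigator's caseloads". Feasibility and a statistical justification can coexist, so that sentence contradicts nothing.
- A reader might ask for power on BMAC against both comparators at once. The plan states no joint success rule, so only pairwise figures apply.

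The SD could also be smaller than 10. At either SD reported in Aim 1, power at 6 points still falls short of 90%. It could equally be larger, which weakens the 12.8-point case.

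**Conclusion.** The concern holds as a failure of reasoning, not of calculation. The closing sentence is wrong as written because the size it calls appropriate fails one of the two scenarios offered in its support. At SD 10, the planned arms can exclude ODI differences of roughly 11 to 12 points between two groups with good power, but not 6. The shortfall for 6 points is 177 evaluable patients needed against about 51 expected.

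These powers rest on TOST at one-sided 0.05, a true difference of 0 and the plan's assumed SD. The 6-point conclusion holds at every SD the plan reports. The 12.8-point conclusion depends on the SD being near 10, and whether 12.8 is a meaningful margin is open given the improvement Aim 1 expects. The primary comparison of CT fusion is not affected by this point. It should be fixed, because it determines what the trial may say about ODI.

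**What to change.** Replace the last sentence of the Sample Size Justification with:

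> The total is 60 patients (20 per arm, about 17 evaluable). Assuming SD 10, a true difference of 0 and TOST at one-sided 0.05, power per pairwise comparison is 98% (20 per arm) or 96% (17) for equivalence within 12.8 ODI points, and 18% or 10% within 6 points; the 6-point scenario is not supported. If the SD is 12, power at 12.8 points falls to 90% or 84%; if 15, to 69% or 57%.

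Name one ODI margin in advance. Give its time point (the hypothesis section says 24 months) and its scale: the inclusion criterion, "ODI v2.1 score > 30", is in percent, while the 12.8 margin and Aim 1's ODI values carry no unit. Justify the margin against the 6.67-point improvement that Aim 1 expects.

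In Aim 1, report pairwise ODI differences with 90% confidence intervals against that margin beside the planned t-tests, and state that a non-significant t-test will not be read as equivalence.

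The cost is wording, one named margin and the added intervals. No patients or visits are added. The downside is a less favourable stated power for ODI.
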